7.3 Study Endpoints

The primary endpoint is the difference in the change in the rating of mouth dryness between MucoPEG and Biotene Dry Mouth Gentle Oral Rinse. The rating of mouth dryness is assessed using the Visual Analogue Scale. Its change is the difference between the assessment before using any of the products, on the first day of a treatment period (on Visit 2 and Visit 5), and after the last dose of a product, on the final day of a treatment period (on Visit 4 and 7).

Patients will also be asked to rate the relief of discomfort of dry mouth using the Dry Mouth Relief Questionnaire. The difference in the proportion of patients giving a response of “4 – Very Good” or “5 – Significant/Excellent” between MucoPEG™ and Biotène® Dry Mouth Gentle Oral Rinse will be examined.

The secondary endpoints include examination of the temporal changes in the effect of MucoPEG relative to Biotene, measured using the Visual Analogue Scale, after using the products for two hours (at Visit 2 and Visit 5) and one week (at Visit 3 and Visit 6). Other **secondary endpoints** include assessment of mouth dryness using Product Performance and Attributes Questionnaire (PPAQ - 4 parts), and Post-Product Use Questionnaire (PPUQ) and the Dry Mouth Inventory (DMI).

Data from these sources will be summarised descriptively.

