9.3 Visit 2 (Baseline Visit)

The second visit will be the Baseline Visit and should occur 1 (+2) days after screening visit and could last up to 4 hours as it will collect pre-use and post-use information at multiple timepoints (5 min, 30 min, 60 min, 120 min, and 240 min).

Before starting any treatment, the following pre-use measurements must be assessed by the Investigator or designated study staff:

- Visual Analogue Scale (VAS)
- Oral Tissue Exam using the Challacombe Scale Score
- Intra-Oral Photo

Before starting any treatment, the following pre-use measurement must be completed by the patient:

- Dry Mouth Inventory (DMI)

Patients will not be allowed to eat or drink during the study visit except for when directed by study staff.

Once the VAS, DMI, the Oral Tissue Exam and Intra-Oral photo have been completed, the sealed envelope will be opened, and treatment order noted. The patient will then self-administer the first dose of the treatment into their mouth using the first sample assigned based on the randomization card.

The **post-use measurements** will include the following at the appropriate timepoints:

- 5 (+ 5) minutes after 1st dose: PPAQ1 (Questions 1-3; completed while patient is in clinic)
- 30 (± 10) minutes after 1st dose: PPAQ2 (Questions 1-11; completed while patient is in clinic)
- 60 (± 10) minutes after 1st dose: PPAQ3 (Questions 12-14; completed while patient is in clinic)
- 120 (± 10) minutes after 1st dose: VAS, Dry Mouth Relief Questionnaire (DMRQ), and PPAQ3 (Questions 12-14; completed while patient is in clinic)
- 240 (± 10) minutes after 1st dose: PPAQ3 (Questions 12-14; completed while patient is in clinic or completed at home)

Other Assessments/Schedule of Events that must be completed during Visit 2 include:

- Provide the patient with a patient diary and instructions as indicated below
- Review any changes in concomitant medications
- Review any side effects/adverse events
- Provide the patient with instructions to use the product at home
- Schedule the next follow-up visit (Visit 3) and instruct patients NOT to take the product the morning of Visit 3

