2.3 Primary Endpoints

- The difference between MucoPEG and Biotène Dry Mouth Gentle Oral Rinse in the change in rating of mouth dryness.

Mouth dryness will be measured using the Visual Analogue Scale:

- VAS (before), which is measured before using any of the products on the first day of each treatment period, at Visit 2 or Visit 5
- VAS (end), which is measured after the last dose of a product on the final day of each treatment period, at Visit 4 or Visit 7

Change in the rating of mouth dryness is the difference between the two time points, that is, VAS (end) – VAS (before).

- The difference between MucoPEG and Biotène in the relief of sensation of mouth dryness between Visit 2 and Visit 4 in the first treatment period and between Visit 5 and Visit 7 in the second treatment period.

This will be measured using the Dry Mouth Relief Questionnaire to evaluate the proportion of patients giving a response of “4 – very good” or “5 – significant / excellent”.

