5.6 Analysis of Study Endpoints

5.6.1 Primary Analysis

The primary endpoint will be examined in the following hypothesis:

- Null hypothesis
Change in VAS after MucoPEG minus change in VAS after Biotène ≥ 0
- Alternative hypothesis
Change in VAS after MucoPEG minus change in VAS after Biotène < 0

Statistical Analysis Plan		Page 15 of 17
Sponsor SunBio Inc.	Study Clinical Evaluation of MucoPEG for Xerostomia	Version 1.1

The change in VAS associated with each product will be calculated as the value of VAS at two hours after the final dose at Visit 4 minus the value of VAS before the first dose at Visit 2 for the first treatment period. Since the Visual Analogue Scale is constructed such that 0 = no symptom and 10 = most severe symptom, an improvement in symptom is represented by a negative change in its measurement. The hypotheses are to test whether patients would experience greater improvement in their symptoms after a course of MucoPEG.

The change in VAS for the second treatment period will be calculated in a similar way from the value of VAS before the first dose at Visit 5 and the value of VAS at two hours after the final dose at Visit 7.

This set of hypotheses will be tested in a one-sided test of difference between two means, for each treatment period, to examine whether a greater change in VAS is associated with MucoPEG than with Biotène. Interval estimation will be carried out using the t distribution and the objective will be met if the upper limit of a 90% confidence interval of the difference is less than zero.

The primary endpoint will also be examined in the following hypothesis:

- Null hypothesis
The proportion of patients with a favourable response after MucoPEG minus the proportion of patients with a favourable response after Biotène ≤ 0
- Alternative hypothesis
The proportion of patients with a favourable response after MucoPEG minus the proportion of patients with a favourable response after Biotène > 0

The numerator will be the number of patients who responded with “4 – very good” or “5 – significant / excellent” in the Dry Mouth Relief Questionnaire. The denominator will be the number of patients eligible for taking the Dry Mouth Relief Questionnaire. Patients with missing outcome status will be reported as a separate category. Change in proportions between Visit 2 and Visit 4 in the first treatment period and between Visit 5 and Visit 7 in the second treatment period will be assessed.

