This set of hypotheses will be tested in a one-sided test of difference between two proportions, for each treatment period, to examine whether a greater proportion is associated with MucoPEG than with Biotène. Interval estimation will be carried out using an exact method for binomial outcomes and the objective will be met if the lower limit of a 90% confidence interval of the difference is greater than zero.

The endpoint will be evaluated by analysing the data from the intent-to-treat set. The endpoint will be presented as the mean difference in scores and its one-sided confidence interval for change in VAS and as mean difference in proportions for ratings from the Dry Mouth Relief Questionnaire.

Statistical Analysis Plan		Page 16 of 17
Sponsor SunBio Inc.	Study Clinical Evaluation of MucoPEG for Xerostomia	Version 1.1

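### SAP 5.6.1 does not say which period result decides success on VAS or DMRQ, and its DMRQ test, read by period, falls far short of the stated 80% power

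*SAP*

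**What the plan says.** SAP 5.6.1 treats the two outcomes in parallel. For VAS: "This set of hypotheses will be tested in a one-sided test of difference between two means, for each treatment period". The objective is met when the upper 90% confidence limit of the difference is below zero. For DMRQ: "This set of hypotheses will be tested in a one-sided test of difference between two proportions, for each treatment period", and the lower 90% limit must exceed zero. Neither rule names a period, and nothing says whether one or both endpoints must succeed. SAP 5.1.4 adds only a general 0.05 level. Protocol 15.3 also frames its t-test by treatment period.

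Other places suggest a single comparison. Protocol 15.1 describes a per-patient difference after both products, Protocol 15.4 has one t-test with no period mentioned, and SAP 5.6.1 closes in the singular: "The endpoint will be presented as the mean difference in scores and its one-sided confidence interval for change in VAS". None of these defines a paired or period-adjusted test. SAP 5.6.3 does combine periods, but only descriptively, within product and for secondary endpoints.

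The DMRQ endpoint appears in two forms. Protocol 7.3 compares products directly ("The difference in the proportion of patients giving a response of" 4 or 5), as do the hypotheses in SAP 5.6.1. But SAP 2.3 describes a difference "in the relief of sensation of mouth dryness between Visit 2 and Visit 4 in the first treatment period", and SAP 5.6.1 adds "Change in proportions between Visit 2 and Visit 4 in the first treatment period", with Visits 5 and 7 handled likewise.

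On endpoint status, Protocol 7.3 says "The primary endpoint is the difference in the change in the rating of mouth dryness between MucoPEG and Biotene" and Protocol 15.1 agrees. SAP 2.3 lists VAS and DMRQ together as primary.

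**The concern.** Within one period each patient uses one product. A by-period test is therefore a comparison of randomization groups, about 19 v 19, and makes no use of the crossover. Two such tests per endpoint with one undifferentiated criterion leave four readings open: period 1 decides, period 2 decides, either suffices, or both are required. The same data can pass under one and fail under another. SAP version 1.1 was written after database lock, so any rule supplied now is chosen late.

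For DMRQ there are two further problems. The sample size appears to assume a within-patient analysis that SAP 5.6.1 does not specify. And the change-between-visits wording has no true baseline. At Visit 2 the only DMRQ is the one 120 "minutes after 1st dose: VAS, Dry Mouth Relief Questionnaire (DMRQ), and PPAQ3" (Protocol 9.3), so a Visit 2 to Visit 4 change would subtract the relief given by the first dose.

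**Working it through.** **Inputs from SAP 4.** VAS: difference -1.25, SD 1.50, one-sided 0.05, 38 effective patients (19 per sequence), 80% power. DMRQ: difference 0.20, SD 0.45, error 0.05, 32 patients, 80% power. SAP 4 does not give sidedness for DMRQ; the test in SAP 5.6.1 is one-sided. The correlation ρ between a patient's two period results is not in the documents and is assumed.

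**Reproducing the VAS size.** For an unpaired test in one period, SE = 1.5 × √(2/19) = 0.487. The noncentral t with 36 df and noncentrality 1.25/0.487 = 2.57 gives 80.9% power. The 38 therefore matches a single-period between-group test.

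**Reproducing the DMRQ size.** One-sample or paired, one-sided: n = ((1.645 + 0.842) × 0.45/0.20)² = 31.3, hence 32. A two-group test needs twice that in each group: 2 × 31.3 = 62.6, so 63 per group. Only the paired one-sided form gives 32.

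**VAS under each unwritten rule.** The two period differences use the same patients with products reversed, so they correlate at -ρ. The table is from 200,000 simulated trials per ρ (first three rows) and the noncentral t (last row). The single contrast is the average of the two period differences, with SE = 0.487 × √((1-ρ)/2).

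| ρ (assumed) | -0.2 | 0 | 0.3 | 0.5 | 0.7 |
|---|---|---|---|---|---|
| Either period suffices: false success | 9.5% | 9.7% | 10% | 10% | 10% |
| Both required: power | 67% | 65% | 64% | 63% | 62% |
| Periods disagree at the planned effect | 28% | 31% | 35% | 36% | 38% |
| Single contrast: SE | 0.377 | 0.344 | 0.288 | 0.243 | 0.188 |
| Single contrast: power | 95% | 97% | >99% | >99% | >99% |

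**DMRQ by period.** At 19 v 19, SE = s × √(2/19). With s = 0.45, SE = 0.146 and power is 38%; with s = 0.49, SE = 0.159 and power is 34%. Full enumeration with an unconditional exact interval gives 27-35% for assumed Biotène rates of 20-60%.

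**DMRQ paired at N = 38.** If 0.45 is the SD of within-patient differences, power is 85%. If it is the SD of a single response, the SD of differences is 0.45 × √(2(1-ρ)) = 0.636, 0.532 and 0.450 at ρ = 0, 0.3 and 0.5, and power is 60%, 73% and 85%. There is a ceiling. A mean difference of 0.20 needs at least 20% discordant pairs, so the SD of differences is at least √(0.20 - 0.04) = 0.40 and power is at most about 92%. Yes/no responses 20 points apart cannot correlate above 0.67 (0.61 for 20% v 40%).

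**Carryover in the single contrast.** Suppose residual MucoPEG effect lowers group A's pre-dose VAS at Visit 5 by c and is gone by Visit 7. The period 2 difference then shifts by c, and the combined contrast by c/2, toward MucoPEG. For assumed c = 0.25 or 0.5 points, false success is 10-16% or 18-37% (ρ from 0 to 0.7). Period 1 is unaffected.

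**The case against.** The strongest reply is that one overall comparison was intended and that the reference to each period only describes how changes are calculated. Protocol 15.1 and 15.4 and the singular closing sentence of SAP 5.6.1 support that. On that reading the either/both problem disappears. What remains is that no such comparison is specified, while the VAS size and SAP 4's reference to a difference between randomization groups fit the by-period test.

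A second reply concerns the remedy. Protocol 5 describes a covalent bond with oral epithelium and the washout is one week, so a pooled contrast could be less robust than period 1 alone. This stands: the crossover contrast is the standard choice, not the only valid one.

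Third, the protocol synopsis, Protocol 7.1 and 15.4, and SAP 2.1 already treat both endpoints as primary. If both must succeed, there is no error inflation across endpoints. This also stands, so a fixed order with VAS first is one option, not a requirement.

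Stronger inferences are not supported. A reader might conclude that the VAS trial is undersized; it is not, and failing to pair only loses efficiency. A reader might also infer that a success rule was picked from the primary results. The SAP version history says only that the hypotheses were corrected after lock and that the sponsor had examined some secondary VAS results.

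**Conclusion.** The point holds. The most natural reading of SAP 5.6.1 and Protocol 15.3, though not the only one, is a separate between-group test per period with no rule for which result decides. On the plan's VAS figures, and an assumed correlation of -0.2 to 0.7, the missing rule moves one-sided error from 5% to as much as 10%, or power from 81% down to 62-67%. It would settle the outcome in roughly a third of trials in which the planned effect is real.

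The DMRQ power statement does not belong to the test described, whose power is about 34-38% (27-35% with an exact interval). A within-patient analysis reaches 85% only if 0.45 is the SD of differences, or if responses correlate at about 0.5. DMRQ did not set the trial's size, so this is a matter of restating power and aligning the test. The two definitions of the DMRQ endpoint must be reconciled whichever analysis is chosen.

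**What to change.** 1. **VAS.** Name one deciding result. The standard choice is a single product contrast over both periods (product, period and sequence fixed, patient random), judged on its 90% interval, with period 1 alone shown as the carryover check. The model keeps patients who have only one period, consistent with Protocol 11.1 and 19.2. Its cost is the carryover sensitivity above. If by-period tests are kept, letting period 1 decide (81% power) or requiring both periods (62-67%) also controls error. Rule out either period sufficing.
2. **DMRQ endpoint and test.** If the end-of-period response is meant, say so and name the 120-minute assessment at Visits 4 and 7, since both visits also have a pre-use DMRQ (Protocol 9.5, 9.8). Analyse it within patient with period adjustment. Add an exact check, because a t-based interval would replace the exact one in SAP 5.6.1 (simulated error 4.8-5.8%). Report the period 1 comparison too, so that data from one-period patients are shown.
3. **DMRQ power.** Restate it for the test used, and say which SD 0.45 is.
4. **Combination.** State that both endpoints must succeed, or fix an order, and align Protocol 7.3 and 15.1 with SAP 2.3. Requiring both lowers power; a fixed order forfeits the second claim if the first fails.
5. **Consistency and labelling.** Align Protocol 15.3 and 15.4 with SAP 5.6.1. Label the rule post hoc and report the per-period results with equal prominence.

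This takes document wording and a few lines of code, with no new patients or data. No change made after lock can fully restore confirmatory error control.

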5.6.2 Sensitivity Analysis

If the proportion of missing responses in the primary endpoints exceeds 5%, we may consider imputing every missing response in favour of Biotène. The same method as outlined in section 5.6.1 will be used for analysing the imputed datasets and the results will be compared to assess the robustness of our conclusions against missing responses.

5.6.3 Secondary Endpoints

Data on each of the secondary endpoints will be summarized descriptively by each product and by treatment period and study site. Estimates of statistics will be presented with their confidence intervals for:

1. The effect of MucoPEG in period 1
2. The effect of MucoPEG in period 2
3. The effect of MucoPEG, combining period 1 and 2
4. The effect of Biotène in period 1
5. The effect of Biotène in period 2
6. The effect of Biotène, combining period 1 and 2

Continuous endpoints such as change in the rating of mouth dryness, measured as the change in VAS, will be summarized as mean, standard deviation, median, minimum, maximum, and number of evaluable observations. Categorical endpoints such as responses in Product Performance and Attributes Questionnaire, Post-Product Use Questionnaire and Dry Mouth Inventory will be summarized as frequency counts and percentages.

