	
10. Participation in another clinical study (including studies of cosmetic products) or in receipt of an investigational drug within 14 days of the screening visit11. Previous participation in this study12. Recent history (within one year prior to screening visit) of alcohol or other substance abuse
Target Population/ Sample Size	42 adults in total for the entire study, males and females
Number of site(s)	Up to 2 sites in the United States
Study Duration	Approximately six months
Participant Duration	The study duration for each participant is expected to be approximately 42 days.
Statistical Methods	
Descriptive summaries will be produced for the primary endpoints and the secondary endpoints using data from the intent-to-treat analysis population.
 
Hypothesis testing for the primary endpoints will be carried out using data from the intent-to-treat analysis population and, as a sensitivity analysis, from the per protocol analysis population.
 
Hypothesis tests will be carried out using data on:
 
• the difference in the mean change in VAS for dry mouth• the difference in the proportion of patients rating the relief of dry mouth as “very good” or “excellent” in the Dry Mouth Relief Questionnaire (DMRQ).

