15.3 Statistical Methods

Data will be summarised descriptively as tables and/or graphs. Continuous variables such as patient’s assessment of mouth dryness using the Visual Analogue Scale (VAS) are to be summarised as mean, standard deviation, number of non-missing observations, median, minimum and maximum by the product used (MucoPEG™ or Biotène® Dry Mouth Gentle Oral Rinse) and period (1 – before washout or 2 – after washout). Discrete variables such as ordinal

responses or binary responses (yes or no) from the Dry Mouth Relief Questionnaire, the Product Performance and Attributes Questionnaire, etc. are to be summarised as frequency counts and percentages by product and period.

Measurements of symptom severity will be tested in a Student's t test for the difference between MucoPEG™ and Biotène® Dry Mouth Gentle Oral Rinse in their mean changes in Visual Analogue Scale for each treatment period. Changes between Visit 2 and Visit 4 and between Visit 5 and 7 will be tested for the primary endpoint and changes between Visit 2 and Visit 3, between Visit 5 and Visit 6, within Visit 2 (before the first dose and two hours after the first dose) and Visit 5 (before the first dose and two hours after the first dose) will be tested for the secondary endpoint. Confidence intervals will be presented with significance probability of the difference between the mean values.

Data on other secondary endpoints will be summarised descriptively.

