15.4 Analysis of Clinical Data

The intent-to-treat (ITT) analysis population is define as all patients enrolled in the study. Patients in this analysis population will be analyzed according to the group to which they were randomized. The per protocol (PP) analysis population is a subset of the ITT population and excludes those patients with a protocol deviation that could affect the measurement of the primary endpoint. For example, a patient who uses over the counter products for dry mouth during the course of the study.

Descriptive summaries will be produced for the primary endpoints and the secondary endpoints using data from the intent-to-treat analysis population.

Hypothesis testing for the primary endpoints will be carried out using data from the intent-to-treat analysis population and, as a sensitivity analysis, from the per protocol analysis population. The change in VAS associated for each product will be estimated as the value of VAS at the end of a treatment period minus the value of VAS before the first dose in the same period. The difference in mean change in VAS for dry mouth between MucoPEG™ and Biotène® Dry Mouth Gentle Oral Rinse will be tested in a Student's t-test. The difference in the proportion of patients rating the relief of dry mouth as "Very Good" or "Significant / Excellent" will be tested in a binomial test of difference between two proportions. We will consider using statistical methods that are more suitable for smaller sample sizes (for example: exact binomial test, bootstrapping) if they are applicable.

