2.2 Secondary Objective

- To evaluate the effect of MucoPEG relative to that of Biotène Dry Mouth Gentle Oral Rinse, using the Visual Analogue Scale, after two hours and one week of use.
- To compare the effect of MucoPEG in treating symptoms of dry mouth to that of Biotène Dry Mouth Gentle Oral Rinse, using the dry mouth Product Performance and Attributes Questionnaire (PPAQ) and the Post-Product Use Questionnaire (PPUQ).
- To evaluate the clinical safety of MucoPEG.
- To examine change in the symptoms of xerostomia using the Dry Mouth Inventory (DMI).

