2.4 Secondary Endpoints

- The difference between MucoPEG and Biotène Dry Mouth Gentle Oral Rinse in the change in rating of mouth dryness.

Mouth dryness will be measured using the Visual Analogue Scale:

- VAS (before), which is measured before using any of the products on the first day of each treatment period, at Visit 2 or Visit 5

Statistical Analysis Plan		Page 10 of 17
Sponsor	Study	Version
SunBio Inc.	Clinical Evaluation of MucoPEG for Xerostomia	1.1

- VAS (after), which is measured two hours after using any of the products on the first day of each treatment period, at Visit 2 or Visit 5
- VAS (1 week), which is measured after the last dose of a product at one week in each treatment period, at Visit 3 or Visit 6

Change in the rating of mouth dryness is the difference from before the products were used, that is, VAS (after) – VAS (before) and VAS (1 week) – VAS (before).

- Assessment of mouth dryness using the Product Performance and Attributes Questionnaire (PPAQ):
 - PPAQ1, PPAQ2 and PPAQ3 at Visit 2, 3 and 4 in Period 1 and at Visit 5, 6 and 7 in Period 2. Patients are to be assessed using PPAQ1 once at 5-10 minutes after administration of the product in each visit, PPAQ2 once at 30±10 minutes, and PPAQ3 three times at 60±10 minutes, 120±10 minutes and 240±10 minutes at each visit.
 - PPAQ4 at Visit 3, 4 in Period 1 and Visit 6, 7 in Period 2.
- Assessment of mouth dryness using the Post-Product Use Questionnaire (PPUQ) at Visit 4 in Period 1 and at Visit 7 in Period 2.
- Assessment of mouth dryness using the Dry Mouth Inventory (DMI) at Visit 2, 3 and 4 in Period 1 and at Visit 5, 6 and 7 in Period 2.

3 Study Design

This study is a randomized, open-labelled crossover trial. Each patient will receive both MucoPEG and Biotène Dry Mouth Gentle Oral Rinse. This study will take place in up to two study sites.

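### SAP 5.6.3 plans no MucoPEG minus Biotène difference for the two-hour and one-week VAS change, although SAP 2.4 defines the endpoint as that difference and Protocol 15.3 says it will be tested

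*SAP*

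**What the plan says.** **Objective and endpoint.** The first secondary objective in SAP 2.2 is the effect of MucoPEG relative to Biotène, "using the Visual Analogue Scale, after two hours and one week of use". SAP 2.4 defines the matching endpoint as "The difference between MucoPEG and Biotène Dry Mouth Gentle Oral Rinse in the change in rating of mouth dryness", with change taken from the pre-dose value at the start of each period to two hours and to one week.

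**Protocol analysis.** Protocol 15.3 specifies a Student's t test between the products in each treatment period. It names the two-hour and one-week changes as tested for the secondary endpoint. It adds: "Confidence intervals will be presented with significance probability of the difference between the mean values". The remaining endpoints are set apart: "Data on other secondary endpoints will be summarised descriptively".

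**SAP analysis.** SAP 5.6.3 opens with "Data on each of the secondary endpoints will be summarized descriptively by each product and by treatment period and study site". It then lists six estimates with confidence intervals: MucoPEG in Period 1, in Period 2 and combined, and the same three for Biotène.

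**Other protocol text.** Protocol 7.3 ends its endpoint section with "Data from these sources will be summarised descriptively". Protocol 15.4 says "Descriptive summaries will be produced for the primary endpoints and the secondary endpoints using data from the intent-to-treat analysis population" and then assigns analysis populations to hypothesis testing of the primary endpoints. The synopsis introduces its list with "Hypothesis tests will be carried out using data on", followed by the two primary measures.

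**The concern.** The SAP defines a comparative endpoint and then plans no output that compares the products on it. It also leaves out a between-product analysis that the protocol states, without recording this as a change.

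The open details are the form of the contrast, the confidence level, and whether the contrast is a test or an estimate. They matter more than usual here because of timing. The SAP version history shows that version 1.1 was written after database lock. It also shows that the reference value for this same endpoint was set after the sponsor had examined results calculated another way. A contrast first specified at the reporting stage would be specified with the data known.

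**Working it through.** **1. Compare the passages.**

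| Place | Two-hour and one-week VAS change |
|---|---|
| SAP 2.2, 2.4 | Defined as MucoPEG versus Biotène |
| Protocol 15.3 | t test between products, each period, with interval and p-value for the difference |
| SAP 5.6.3 | Descriptive; 2 products × (Period 1, Period 2, combined) = 6 estimates, 0 contrasts |
| SAP version 1.1 change list | Records a new reference value for this endpoint; does not mention loss of the test or contrast |

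The word effect in SAP 5.6.3 cannot mean the between-product difference, because each product has its own entry for the same period. SAP 5.6.1 does specify a difference with a 90% interval, but only for the primary endpoints.

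**2. Confidence level.** SAP 5.6.3 gives none. SAP 5.1.1 names the t-distribution without a level. SAP 5.1.4 sets a default significance level of 0.05 for tests, which does not settle the level of a descriptive interval.

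**3. The plan's own figure.** The documents state no sample size or SD for this endpoint. For the primary VAS change, SAP 4 gives a difference of -1.25, SD 1.50, one-sided 0.05, 80% power and 38 patients. An exact two-sample t calculation gives 80.9% power with 19 per sequence (38 in total) and 79.0% with 18 (36 in total). The stated 38 is therefore reproduced as a comparison of two independent groups of 19.

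**4. What can be rebuilt from the planned tables.** Within a period, different patients use each product, so the difference follows from the reported mean, SD and n of each group. Illustration with 19 against 19 and the primary SD of 1.5, assumed to carry over:

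- SE = 1.5 × √(2/19) = 0.487
- df = 19 + 19 − 2 = 36; t(0.975) = 2.028; t(0.95) = 1.688
- 95% half-width = 2.028 × 0.487 = 0.99
- 90% half-width = 1.688 × 0.487 = 0.82

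If the SD is between 1.0 and 2.0, the 95% half-width runs from 0.66 to 1.32.

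**5. Number of tests if Protocol 15.3 is restored.** Two time points × two periods = 4 tests. At 0.05 each, the chance of at least one false positive would be 1 − 0.95⁴ = 18.5% if the tests were independent. They share patients and pre-dose values, so this is a reference figure only.

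**The case against.** **Little is lost.** The per-period differences are the only contrasts that Protocol 15.3 planned for this endpoint, and a reader can rebuild them from the planned summaries. This stands and limits the size of the point. It does not remove it: the SAP should report its own endpoint, and whether the endpoint is tested remains undecided.

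**The protocol may have intended description.** A reader might infer that the protocol contradicts itself, with 15.3 testing the endpoint and 7.3, 15.4 and the synopsis confining it to description. The documents do not support that. The descriptive sentence in 15.4 also covers the primary endpoints, which are tested, so description there does not exclude testing. Section 15.4 and the synopsis are silent on secondary testing. In 7.3 the closing sentence comes directly after the questionnaires and may refer to them alone, which would agree with the split in 15.3. It is ambiguous at most. None of these passages resolves the mismatch between Protocol 15.3 and SAP 5.6.3.

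**Two further inferences go too far.** A reader might suppose that the test was dropped because of the results. SAP version 1.0 is not among the documents, so when the contrast was lost is unknown. A reader might also count the absence of a combined within-patient difference as a departure. Neither document planned one for this endpoint.

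**Conclusion.** The point holds as a mismatch between the SAP's endpoint definition and its analysis, and as an unrecorded departure from Protocol 15.3. The mismatch rests on the text alone and needs no numerical assumption.

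Its consequence is modest. The missing per-period differences are recoverable. The precision illustration assumes 38 completers split equally between sequences and borrows the SD from the primary endpoint. The primary analysis in SAP 5.6.1 has its own between-product difference, so neither the primary conclusion nor the sample size is touched. The correction should be made, but the trial does not depend on it.

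**What to change.** 1. In SAP 5.6.3, add the MucoPEG minus Biotène difference in VAS change at two hours and at one week, for each treatment period, with a confidence interval at a stated level. This restores what Protocol 15.3 planned.
2. State whether the difference is tested or only estimated. If tested, note that there are four tests, and either call the p-values nominal or give a multiplicity rule.
3. Disclose beside these rows that SAP version 1.1 set the reference value for this endpoint after database lock and after the sponsor had examined results.
4. If description only is intended, record that as a change from Protocol 15.3, with the reason.
5. Clarify which data the closing sentence of Protocol 7.3 covers.
6. A combined within-patient difference is optional. If added, label it post hoc.

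The cost is SAP wording, a clarification of one protocol sentence and a few table rows. No new data are needed.
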